The overall objective of the present research is to use ecological momentary assessment (EMA), a real-time, naturalistic data collection method, to prospectively study the impact of reduced cannabis use on functional outcomes in heavy cannabis users. EMA addresses several limitations of traditional assessment techniques by enhancing ecological validity, minimizing memory bias, and enabling examination of the impact of context on participants' behavior. Our central hypothesis is that reductions in frequency and quantity of cannabis use will lead to positive changes in cannabis users' functional outcomes. The rationale for this research is that it will provide real-time data concerning the impact of reductions in cannabis use on functioning and will support efforts to include reductions in illicit drug use as a valid outcome measure in pharmacotherapy studies (Tiffany et al., 2011; Donovan et al., 2011).

Contingency management (CM) will be used to promote reductions in frequency and quantity of cannabis use. CM is an intensive behavioral therapy that is highly effective at producing short-term reductions in illicit drug use. Moreover, we have developed a novel approach that leverages mobile technology and recent developments in cannabis testing to make daily CM for cannabis more portable and feasible. We have pilot-tested this approach with heavy cannabis users and found that it is an acceptable and feasible method to reduce cannabis use. The present research will use this technology in conjunction with state-of-the-art EMA methods to study the impact of reduced cannabis use on key functional outcomes.

We will pursue the following specific aims during the R21 phase:

R21 Aim 1: Refine the study procedures and the CM reinforcement schedule to ensure that a majority of participants will be adherent, find the study procedures acceptable, and substantially reduce their frequency and quantity of cannabis use.

Milestone 1: The majority (i.e., $\geq 65\%$) of participants will be adherent and rate procedures as acceptable.

Milestone 2: We will identify a CM reinforcement schedule that reliably produces $\geq 50\%$ reductions in frequency and quantity of cannabis use among at least half of the heavy cannabis users enrolled.

R21 Aim 2: Examine the association between days of cannabis use and total amount of cannabis used.

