to stress, trauma, and coping strategies. Participants will be informed about these new study procedures verbally, and the study team member who informs them will provide a note-to-fil indicating so. Participants can refuse to complete these measures. We will ask ongoing participants to complete these measures at their next study visit or follow-up session. When study enrollment begins again, participants will complete these measures at the screening session. We are adding the CAIR Pandemic Impact Questionnaire (Lang, 2020; https://www.nlm.nih.gov/dr2/CAIR-PIQ_scoring.pdf), and another measure, COVID Core Questions, with variables of interest. If a participant endorses any item marked with an asterisk on the COVID Core Questions measure, we will ask them to complete a PTSD Checklist 5 related to that specific event. Finally, we have added a measure designed to evaluate participants' satisfaction with remote study procedures.

E. DATA ANALYSIS PLAN

Multilevel modeling (MLM) will be used to analyze the EMA data. MLM is a technique for analyzing repeated observations of data across multiple individuals. Unlike repeated-measures ANOVA, MLM can incorporate time-varying (Level-1) and time-invariant (Level-2) predictors. MLM can also accommodate imbalanced data and unequal variances. The main conclusions drawn from this study will be based on the pre-specified hypotheses, which will be tested with two-sided statistical tests at an alpha of .05. Analyses will be performed with SAS for Windows (Version 9: SAS Institute, Cary, NC).

E.1. Missing Data.

Although we do not anticipate much missing baseline data, we do anticipate missing values in the EMA data. MLM procedures, which will be used to analyze H_{1A}, H_{1B}, and the supplementary aim, are based on maximum likelihood estimation and use all available data. As such, MLM can accommodate data missing at random. Missing data will be examined to determine whether missingness is random or systematically associated with baseline variables. Those baseline parameters associated with missingness will be covaried. If data are suspected to be missing not at random (i.e., only certain values are likely to be missing), multiple imputation will be used to analyze non-random patterns of missing EMA data (Schafer & Graham, 2002).

E.2. Electronic Diary Compliance and EMA Data Reduction.

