During the 8-week EMA data collection, we will calculate the percentage of responses recorded within 5 minutes of the random prompts. We will exclude responses delayed by longer than 5 minutes from the analyses. Data will be aggregated at the day-to-day level to indicate the following: whether cannabis was used; the total number of joints/grams consumed; mean daily potency; mean daily levels of mental health symptoms, self-efficacy, health-related quality of life, working memory, and impulsivity; whether participants drove while intoxicated; and total amount of physical activity. By using multi-daily records to examine day-level phenomena, we will minimize measurement error related to poor recall and random variability. For the 2-week baseline period and each week of the 6-week experimental period, we will calculate frequency of cannabis use as the number of days used per week. To quantify change in frequency of cannabis use from baseline, change scores will be calculated by subtracting number of days per week of cannabis use during the 2-week baseline from those levels

recorded during each week of the mCM treatment period. A dichotomous variable will also be calculated reflecting whether a given participant achieved at least a 50% reduction in cannabis use during a given week. Thus, the data will be structured such that each participant will have up to 56 rows of data corresponding to each day of the 2-week baseline period and 6-week mCM/non-contingent control. Each row will contain a dichotomous indicator of whether or not cannabis was consumed that day, total quantity of cannabis consumed that day, total THC load of the cannabis used that day, daily estimates of functioning, a baseline estimate of cannabis use, and three variables capturing weekly varying frequency, quantity, and total THC load of cannabis use: the aforementioned dichotomous variable measuring whether a 50% reduction from baseline use was achieved and a change score, with a 0 change-score value for days falling during the 2-week baseline.

E.3. Hypotheses 1a and 1b.

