To examine the effect of reduced cannabis use on functioning assessed with EMA, day-by-day outcome variables will be modeled *via* MLM as a function of treatment group (Level 2), week (Level 1; with the two baseline weeks treated as a single week), and treatment-by-week interactions. Daily consumption (total equivalent number of joints/gram consumed and total potency; Level 1) will be examined as potential covariates. Linear and quadratic time effects will be explored. Week-by-week effects of cannabis reduction will be examined in separate models. We will also examine the effects of reduced use by modeling day-by-day and week-by-week outcomes as a function of week-by-week reductions in cannabis, independent of treatment group. Linear MLM will be used to model normally distributed outcome variables *via* PROC MIXED. Generalized linear MLM will be used to model dichotomous and otherwise non-normally distributed outcome variables *via* PROC GLIMMIX.

E.4. Supplementary Aim.

To examine whether reduced cannabis use moderates or is moderated by other factors (e.g., sex differences), the models examined in Hypotheses 1a and 1b will be modified to include potential Level-1 (e.g., day-to-day craving, sleep) and Level-2 (e.g., sex, baseline cannabis use, self-efficacy) predictors as well as their interactions with week-by-week change in cannabis use. For instance, to determine whether a week-by-week reduction in cannabis use moderates the association of day-by-day cannabis use (or abstinence) with daily working memory, whether or not participants used cannabis that day (Level 1) will be added as a predictor of working memory as will its interaction with week-by-week change in frequency or quantity of cannabis use. This particular model could thus determine whether cannabis users demonstrate greater cognitive functioning on abstinent days when they reduce their cannabis use.

E.5. Power Calculations.

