Power calculations are based on Hypotheses 1a and 1b and were performed with Power Analysis and Sample Size software (PASS, Version 12: NCSS LLC, Kaysville, Utah). We conservatively estimate that as many as 12 participants could potentially need to be excluded due to sustained abstinence, leaving a minimum of 60 participants available for analysis. The corresponding analyses make use of multilevel data with a total sample of up to 3,360 records (60 participants X 56 daily observations). Because there will only be 7 unique estimates per participant of week-to week change in frequency of cannabis use, a conservative minimum estimate of the effective sample size is 420 (60 participants X 7 weekly

observations). Although these observations are non-independent given clustering within participants, hence the use of MLM, accounting for variation between participants will reduce the error variance in the dependent variables. Thus, the effective sample size will very likely exceed 420. An effective sample size of 420 has 90% power to detect small-to-medium treatment effects equivalent to Cohen's $d = 0.30$ or associations equivalent to $r = .16$.

References

Adkisson, K., Cunningham, K.C., Dedert, E.A., Dennis, M.F., Calhoun, P.S., Elbogen, E.B., Beckham, J.C., & Kimbrel, N.A. (manuscript under review). Cannabis use disorder and post-deployment suicide attempts in Iraq/Afghanistan-era veterans.

Babor TF, de la Fuente JR, et al., 1989. AUDIT The Alcohol Use Disorders Identification Test: Guidelines for use in primary health care (WHO/MNH/DAT 89.4). Geneva, Switzerland.

Beckham, J.C., Adkisson, K.A., Hertzberg, J., Kimbrel, N.A., Budney, A.J., Stephens, R.S., Moore, S.D., & Calhoun, P.S. (manuscript under review). Mobile contingency management as an adjunctive treatment for co-morbid cannabis use disorder and cigarette smoking.

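### The secondary reduction model in E.3 (and E.4) gives weekly change one coefficient, so stable differences between people who reduce more and less mix with the within-person effect

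*Combined protocol and SAP*

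**What the plan says.** The central hypothesis in the Specific Aims is that "reductions in frequency and quantity of cannabis use will lead to positive changes" in functioning. Hypotheses 1a and 1b are worded as associations with decreased use.

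E.2 builds the exposure. For frequency, "change scores will be calculated by subtracting number of days per week of cannabis use during the 2-week baseline" from the level in each treatment week. The data row carries "a change score, with a 0 change-score value for days falling during the 2-week baseline", together with an indicator of "whether a given participant achieved at least a 50% reduction in cannabis use during a given week". The same set is planned for quantity and THC load. A baseline-use estimate is also on the row. No person mean of the reduction variables and no deviation from such a mean is listed.

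E.3 opens with the randomised model (group, week and their interaction). It then adds, as a further analysis, "modeling day-by-day and week-by-week outcomes as a function of week-by-week reductions in cannabis, independent of treatment group". E.4 reuses weekly change in its moderator interactions. Sections E.1 to E.5 do not mention centring, a within/between split or person fixed effects, and E.3 does not state the random effects of the reduction model. Hypotheses are to be "tested with two-sided statistical tests at an alpha of .05".

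**The concern.** The weekly change score varies in two ways. Within a person it is 0 in the ad lib weeks and then moves from week to week. Between people, some cut a lot in all six weeks and others hardly at all. Subtracting baseline use removes differences in starting use, but not differences in how much people cut.

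The hypothesis concerns the first kind of variation: when a person reduces, that person functions better. The second kind is open to confounding, because people who manage to reduce may have functioned better all along, ad lib weeks included. A random-intercept model with one coefficient uses both. Because this model sets the arm aside, randomisation does not protect it. A standing difference between larger and smaller reducers could then be reported as support for reduction as an outcome measure in pharmacotherapy trials.

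**Working it through.** **Plan's own figure.** The part of the E.5 power statement that fits this model is r = .16 at an effective N of 420. Power = Φ(atanh(0.16)·√417 − 1.96) = Φ(3.30 − 1.96) = 0.91, so the stated 90% reproduces. It concerns power and says nothing about the false-positive rate.

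**Inputs from the documents.** E.5 plans for exclusions "leaving a minimum of 60 participants available for analysis"; allocation is 2:1 (D.1), taken here as 40:20. E.5 also notes that "there will only be 7 unique estimates per participant of week-to week change in frequency of cannabis use". E.2 gives up to 56 daily rows, 14 of them ad lib and 42 experimental. Alpha is .05, two-sided.

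**Assumptions (not in the documents).** No true effect. Mean change −2.0 days/week (SD 1.7) in Reduced Use and −0.3 (SD 1.0) in control. Week-to-week SD 1.0. Random intercept only, outcome variance 1. Correlation ρ of 0.2–0.4, within arm, between amount reduced and stable functioning. Daily ICC 0.1–0.5.

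**Matching the ICCs.** A weekly mean averages 7 days. With independent daily residuals, weekly ICC = 7d/(1 + 6d). Daily 0.1, 0.2, 0.3 and 0.5 give weekly 0.44, 0.64, 0.75 and 0.88.

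**Spread of the predictor.**
- Person-level variance: (2/3)·1.7² + (1/3)·1.0² + (2/9)·(2.0 − 0.3)² = 2.26 + 0.64 = 2.90. Adding 1.0²/6 gives 3.07 for the six-week mean.
- Mean square of the six-week mean: 1.43² + 3.07 = 5.12.
- Weekly rows: S_B = 7·(6/7)²·3.07 = 15.8; S_W = (6/7)·5.12 + 5 = 9.39.
- Daily rows: S_B = 56·(42/56)²·3.07 = 96.7; S_W = (14·42/56)·5.12 + 35 = 88.8.

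**Formulas.** With T rows per person, λ = (1 − ICC)/(1 + (T − 1)·ICC). The between-person share is λS_B/(S_W + λS_B). The spurious slope is that share times the between-person slope. SE = √[(1 − ICC)/(60·(S_W + λS_B))].

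**Worked cell: weekly rows, daily ICC 0.2 (weekly 0.636), ρ = 0.3.**
- λ = 0.364/(1 + 6·0.636) = 0.0755; share = 1.19/(9.39 + 1.19) = 11.3%.
- Average within-arm SD = (2/3)·1.7 + (1/3)·1.0 = 1.467. Between slope = (6/7)·0.3·√0.636·1.467/[(6/7)²·3.07] = 0.133.
- Spurious slope = 0.113·0.133 = 0.0150; SE = √[0.364/(60·10.58)] = 0.0239; shift = 0.63 SE.
- Rejection = Φ(0.63 − 1.96) + Φ(−0.63 − 1.96) = 0.092 + 0.005 = 9.6%.

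The same steps give these false-positive rates (weekly rows / daily rows):

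| Daily ICC (weekly) | ρ = 0.2 | ρ = 0.3 | ρ = 0.4 |
|---|---|---|---|
| 0.1 (0.44) | 8% / 7% | 13% / 10% | 19% / 14% |
| 0.2 (0.64) | 7% / 6% | 10% / 8% | 13% / 10% |
| 0.3 (0.75) | 6% / 6% | 8% / 7% | 10% / 8% |
| 0.5 (0.88) | 6% / 5% | 6% / 6% | 7% / 6% |

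**Simulation.** Simulated fits with matched ICCs agree, allowing for Monte Carlo error (about √(0.1·0.9/1000) = 0.9 points at a rate of 10% and 1,000 runs). At ρ = 0.3 and daily ICC 0.2, 0.3, 0.4 and 0.5, weekly rows gave about 10%, 10%, 7% and 7.5%; daily rows gave 9%, 8%, 6.5% and 5%. At ρ = 0.2 all cells were 5–8%. A second matched simulation put the ρ = 0.2–0.3 range at about 5–9%. At ρ = 0.4, weekly rows gave 10–17% for daily ICC 0.2–0.4. At ρ = 0 the rate is about 5%.

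With the predictor split in two, the within-person term rejected in 4.4–5.9% of runs on weekly rows and 3.8–6.5% on daily rows. Week indicators alone did not help: at ρ = 0.3 and weekly ICC 0.4, 0.5 and 0.6 the undivided weekly rates were 12%, 15% and 9% without them and 15%, 15% and 11% with them.

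**The case against.** The strongest reply is that this is not the trial's main test. E.3 leads with the randomised model, D.1 rests clear inference on the control group, and the reduction model is introduced as an addition. That stands. A reader might infer that the test of Hypotheses 1a and 1b as a whole has an inflated error rate; the documents do not support this, because the group-by-week comparison does not use the change score. The model is still not trivial, since both hypotheses are phrased as associations with decreased use.

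Second, the deciding input is missing. The pilot range of 18–93% (B.5, four people) shows that reductions differ, not that they track usual functioning. A reader might infer that the error rate will double. The documents support only that it can, under correlations they do not give.

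Third, E.3 is silent on random effects and centring, so the single coefficient under a random intercept is the plain reading of E.2 and E.3 rather than an explicit commitment; other random structures were not examined. The baseline-use estimate on each row might absorb part of the confounding, but E.3 does not commit to entering it.

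Fourth, the split is not a cure. Much within-person variation is ad lib versus treatment weeks, so without week in the model the deviation term can carry time, monitoring and payment effects. This also stands and shapes the fix.

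**Conclusion.** The concern holds for the reduction model in E.3 and the E.4 models that reuse weekly change, as a cheap improvement to a secondary analysis. The plan's variables give one blended coefficient where the hypothesis needs the within-person part.

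Under the stated assumptions the inflation is modest over most of the range: about 5–9% at daily ICC 0.2–0.5 with correlation 0.2–0.3, touching 10% at the edge on weekly rows. It is material, at about 10–20%, for correlation 0.4 at daily ICC 0.1–0.2, or correlation 0.3 at daily ICC near 0.1. It vanishes at zero correlation.

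A between-person share of only 11% does not make the blend harmless, because it multiplies a confounded slope and is judged against a small standard error. The ICC matching assumes independent daily residuals; a week-level variance component would lower the weekly ICC for a given daily ICC and move the weekly rates toward the upper rows of the table. The randomised group-by-week test is unaffected.

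**What to change.** In E.3 and E.4, split each weekly reduction variable (change score and 50% flag, for frequency, quantity and THC load) into the person's mean over his or her rows (Level 2) and the deviation from that mean (Level 1). Enter both, in the E.4 interactions as well. Keep week in these models, so that differences between ad lib and treatment time are not credited to reduction. Because the person mean includes the zero ad lib rows, the deviation still captures the change from ad lib to treatment.

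Report the Level-1 coefficient as the within-person association and the Level-2 coefficient as descriptive. State that causal conclusions rest on the randomised group-by-week contrast.

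The cost is a sentence or two of text and two derived variables per exposure, with no new data. The standard error rises by a factor of 1/√(1 − share). Simulated shares of 24%, 18% and 13% at weekly ICC 0.4, 0.5 and 0.6 give 15%, 10% and 7%; the rise is less at higher ICCs and on daily rows. This is the price of the split alone; any further loss of precision from keeping week is not included. The split removes stable between-person confounding only. Confounding that varies from week to week, and reverse causation, remain and should be named as limitations.

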Eligible participants will be trained in the EMA procedures following established procedures at the end of the baseline assessment (Beckham, Calhoun 2013). Participants will then practice with the electronic diary at home for 24 hours. Once the training period is complete, participants will complete an 8-week EMA study in which they will carry the diaries with them on a daily basis. The first 2 weeks of the EMA study will involve daily assessments of cannabis use and participants' functional outcomes during the *ad lib* period to establish baseline patterns of use. During the *ad lib* period, participants will also be asked to perform self-initiated diary readings when they begin cannabis use. When participants begin the diary reading, the phone will set an alarm for 60 minutes later. When the alarm sounds, the participant will use a saliva test kit and upload the readings. Participants will be paid \$5 once per day if they begin a self-initiated reading on that day. On day 15, participants in the Reduced Use Condition ($n = 48$) will begin reducing their cannabis use through participation in the mobile CM for cannabis protocol, whereas participants in the Control Condition ($n = 24$) will receive non-contingent payments based on the mean of two yoked participants' earnings. All participants will continue to provide EMA assessments of their functional outcomes during the 6-week experimental period so that we can study the impact of reduced cannabis use on functioning. Electronic diary data stored on the smart phone are encrypted at rest. Data will be downloaded from the smart phones to duhsnas-pri\dusom_psych\private\irb\[name]\Marijuana.

Table 3. Description and Timing of In-Person Assessments

| MEASURE | DESCRIPTION | BL | End of ad lib | 8-wk |
|--|---|----|----------------------|------|
| Demographic Assessment | PhenX (Hamilton et al., 2011) protocols will assess age (#010101), race (#010601), ethnicity (#010501), gender (#010700), and sexual orientation (#101401). | X | | |
| Structured Clinical Interview for DSM-5 (First et al., 2015) | Will be used to diagnose CUD and other psychiatric disorders based on DSM-5 criteria in order to determine study eligibility and characterize sample. | X | | |
| Columbia Suicide Severity Rating Scale (Posner et al., 2011) | State-of-the-art interview that assesses the full continuum of suicidal behavior. Will be used to determine study eligibility and assess suicidal behavior. | X | | X |

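### E.5's 90% power for a treatment effect of d = 0.30 does not belong to the treatment-by-week test in E.3, and 420 independent records would not give it either

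*Combined protocol and SAP*

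**What the plan says.** E.5 explains the multiplier of seven: "Because there will only be 7 unique estimates per participant of week-to week change in frequency of cannabis use". It multiplies by the 60 participants left after up to 12 exclusions, calls the result "a conservative minimum estimate of the effective sample size is 420 (60 participants X 7 weekly" observations), and concludes: "An effective sample size of 420 has 90% power to detect small-to-medium treatment effects equivalent to Cohen's $d = 0.30", "or associations equivalent to $r = .16". The general part of section E sets the pre-specified hypotheses, "which will be tested with two-sided statistical tests at an alpha of .05".

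Three other places show what the seven observations are and how they will be used.

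- E.3 models the outcomes on treatment group, "week (Level 1; with the two baseline weeks treated as a single week), and treatment-by-week interactions". The seven are therefore one ad lib period plus six experimental weeks. A second E.3 model relates outcomes to weekly reduction in use, ignoring group.
- E.2 fills in the change score for the ad lib period by definition, "with a 0 change-score value for days falling during the 2-week baseline".
- D.6 places the start of the intervention after that period: "On day 15, participants in the Reduced Use Condition" begin to reduce their use.

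D.1 plans 48 v 24 participants. D.2 says that up to 12 can be left out with adequate power remaining. E.5 acknowledges clustering but gives no within-person correlation and no power for an interaction.

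**The concern.** The count of seven comes from the exposure (weekly change in cannabis use) but is then used for a group effect. In the ad lib period the arms have not yet been treated differently, so one seventh of the 420 records cannot show the effect being powered. E.3 asks whether the groups diverge over the weeks. A pooled comparison of 420 records answers a different question, and its power need not resemble that of the interaction.

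E.5 is the only power statement for the central hypotheses, and the allowance for exclusions in D.2 depends on it. A null result on H1a or H1b could be read as coming from a randomized test with 90% power when no such power has been shown.

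**Working it through.** **Inputs.** From the documents: two-sided alpha .05 (E); d = 0.30, r = .16, 60 participants and 7 observations (E.5); 2:1 allocation (D.1); one ad lib period of 14 days and six experimental weeks (E.2, E.3). Assumed: a split of the 60 as 40 v 20 (2:1 kept) or 36 v 24 (all 12 exclusions from the Reduced Use arm, 48 - 12 = 36); equal correlation rho between weekly values; and d measured in weekly SD.

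**1. The plan's own figures.** 60 x 7 = 420. Treat these as independent.

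- Association: power = Phi(atanh(r) x sqrt(N - 3) - 1.96). With r = .16, 0.1614 x sqrt(417) = 3.296, so power = Phi(1.336) = 90.9%. This reproduces.
- Treatment effect: noncentrality = d / sqrt(1/n1 + 1/n2).

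| Split of 420 | Noncentrality | Power (normal) | Power (noncentral t) | d for 90% |
|---|---|---|---|---|
| 280:140 (2:1) | 2.898 | 82.6% | 82.4% | 0.336 |
| 252:168 (as 36:24) | 3.012 | 85.4% | 85.2% | 0.323 |
| 210:210 (1:1) | 3.074 | 86.7% | 86.6% | 0.316 |

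No row gives 90%. At d = 0.30, 90% would need 468 records at 1:1 or 528 at 2:1.

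**2. The contrast that E.3 implies.** Take the simplest summary of the treatment-by-week effect: the mean of six experimental weeks minus baseline, compared between arms, with a constant effect of 0.30 in all six weeks.

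Variance = (1 - rho) x (1/b + 1/6) x (1/n1 + 1/n2), where b is the number of weeks' precision given to the ad lib period. Power = Phi(0.30 / sqrt(variance) - 1.96).

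- b = 2 if all 14 ad lib days contribute: 1/2 + 1/6 = 2/3.
- b = 1 if the period counts as one week: 1 + 1/6 = 7/6.
- At 40 v 20, 1/40 + 1/20 = 0.075.

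Example, rho = 0.8 and b = 2: variance = 0.2 x 2/3 x 0.075 = 0.010, SE = 0.10, and power = Phi(3.00 - 1.96) = 85%.

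| rho | 40 v 20, b = 2 | 40 v 20, b = 1 | 36 v 24, b = 2 | 36 v 24, b = 1 |
|---|---|---|---|---|
| 0 | 27% | 17% | 29% | 18% |
| 0.5 | 48% | 30% | 50% | 32% |
| 0.7 | 69% | 46% | 72% | 49% |
| 0.8 | 85% | 62% | 88% | 65% |
| 0.9 | 99% | 89% | 99% | 92% |

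**3. Correlation needed for 90%.** Set 0.30 / sqrt(variance) = 1.960 + 1.282 = 3.242. The variance must then be (0.30/3.242)^2 = 0.00856. At 40 v 20, 1 - rho = 0.00856 / (0.075 x 2/3) = 0.171, so rho is about 0.83 for b = 2. For b = 1, 0.00856 / (0.075 x 7/6) = 0.098, so rho is about 0.90.

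**4. Sensitivity to the SD unit.** If d is in daily SD and there is no correlation between days, the variance is (1/14 + 1/42) x 0.075 = 0.00714 and power is Phi(3.55 - 1.96) = 94%.

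**The case against.** The strongest reply is that E.5 never says the ad lib period carries a treatment effect. It counts levels of the exposure, of which E.2 creates exactly seven, and E.3 plans a model on that exposure. This stands. For that association the ad lib rows are legitimate data, and r = .16 reproduces if independence is granted. The reply does not cover the other half of the sentence, where the same 420 is applied to treatment effects.

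E.3 also names no reference week, and it will explore linear and quadratic time, under which baseline is simply the first time point. Baseline as the reference is therefore a reasonable inference, not a stated rule. The contrast above is one summary of the interaction.

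E.2 and E.3 keep daily rows for all 14 ad lib days, and coding two weeks as one does not discard data. The b = 2 columns are therefore fairer to the plan than b = 1, and both are shown.

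E.5's argument that accounting for variation between participants reduces error variance is right in direction for a within-person change: power rises with rho. It does not make 420 a minimum, because E.5 states no correlation and at low or moderate values power is far below 90%.

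A reader might infer that the repair is to drop the ad lib period and write 60 x 6 = 360, with about 76% power at 2:1. The documents do not support that. It would be another pooled comparison of independent records, which E.3 does not fit, and it would discard the baseline that the interaction relies on.

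**Conclusion.** The point holds for the treatment-effect claim. The 420 includes a pre-treatment observation, it describes a pooled comparison and not the E.3 interaction, and at two-sided .05 it gives 82% (2:1) to 87% (1:1) for d = 0.30 even with every record independent.

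For the group difference in change, power runs from 17% to 99% over correlations 0 to 0.9 at 40 v 20. It reaches 90% only at about 0.83 to 0.90. This rests on an assumed split, equal correlation, a constant effect, weekly SD units and a normal approximation.

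Two stronger readings should be resisted. The documents do not show that the trial is underpowered: the correlation and the SD unit are not given, and a high correlation or daily-SD units without week-level variance could exceed 90%. Nor is the whole power section wrong, since the r = .16 statement fits a planned model and reproduces under independence. What is established is that the stated 90% has not been shown for the planned randomized test.

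**What to change.** In E.5, withdraw the statement of 90% power at d = 0.30, and stop describing 420 as a conservative minimum for treatment effects. Do not put 360 or 76% in its place.

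State instead the power, or the effect detectable at 90%, for the treatment-by-week contrast in E.3:

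- at 40 v 20 and at 36 v 24 participants;
- using all 14 ad lib days;
- over a stated range of week-to-week correlation, or with correlations estimated from the R21 EMA data;
- naming the time coding of the contrast and the SD unit in which d is expressed.

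Report the r = .16 association separately, with its independence assumption stated. Then bring the claim of adequate power in D.2 into line with the restated figure.

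The cost is one recalculation and a rewording of E.5 and D.2. The stated power will probably be less favourable. No extra patients are needed.

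### Section E.5 claims 90% power for a treatment effect of d = 0.30 from an effective sample size of 420; the figure is 83 to 87%, and 420 is not shown to be a minimum for the treatment terms

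*Combined protocol and SAP*

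**What the plan says.** E.5 starts from 72 randomised participants and allows up to 12 exclusions for sustained abstinence, "leaving a minimum of 60 participants available for analysis". It counts 60 x 56 = 3,360 daily records, then reduces this to 60 x 7 = 420. The reason given is: "Because there will only be 7 unique estimates per participant of week-to week change in frequency of cannabis use", so that "a conservative minimum estimate of the effective sample size is 420". E.5 acknowledges clustering within participants, expects the multilevel model to lower the error variance, and concludes: "Thus, the effective sample size will very likely exceed 420". The power statement follows: "An effective sample size of 420 has 90% power to detect small-to-medium treatment effects", put at d = 0.30, or at r = .16 for associations.

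Three other places bear on this. Section E rests the main conclusions on pre-specified hypotheses, "which will be tested with two-sided statistical tests at an alpha of .05". D.1 randomises 2:1, 48 to Reduced Use and 24 to Control. E.3 says that "day-by-day outcome variables will be modeled" on treatment group (a Level-2, between-person factor), week, and their interaction. A further set of E.3 models uses weekly reduction in cannabis use as the predictor, regardless of group.

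E.5 does not give the allocation used in the calculation, an intraclass correlation (ICC), the standard deviation that scales d, or the treatment term that d refers to.

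**The concern.** An effective sample size is already the equivalent number of independent observations, so the power at d = 0.30 can be checked without knowing anything about clustering. It does not come out at 90%. The two effects in the sentence are also offered as if interchangeable, yet r = .16 corresponds to a d above 0.30.

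The second issue is what 420 counts. It is the number of weekly values of a time-varying predictor, change in cannabis use. E.5 then applies it to treatment effects, and treatment does not vary within a person. How often a different predictor takes a new value sets no floor on the information about a between-person term.

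At stake is the accuracy of the power statement for the randomised comparison, and whether a reader may treat 420 as a safe lower bound for it.

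**Working it through.** **Inputs.** Two-sided alpha .05 (section E); effective N = 420, d = 0.30, r = .16, 60 participants, 56 days (E.5); allocation 48:24 (D.1). Three splits of 420 are used:
- 2:1, that is 280:140 (exclusions proportional, 40:20 people x 7);
- 36:24, that is 252:168 (all 12 exclusions from Reduced Use, x 7);
- 1:1, that is 210:210, the most favourable split.

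**Step 1: the counts.** 60 x 56 = 3,360 and 60 x 7 = 420. Both reproduce.

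**Step 2: the association.** Fisher z: power = Phi(atanh(.16) x sqrt(417) - 1.96) = 90.9%. This reproduces.

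**Step 3: the treatment effect.** Power = Phi(d x sqrt(n1 n2/(n1 + n2)) - 1.96). Detectable d at 90% = (1.960 + 1.2816) x sqrt(1/n1 + 1/n2). N for 90% at d = 0.30 = (10.507/0.09) x (1/p + 1/(1 - p)), where p is the share in one arm.

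| Split | sqrt(n1 n2/N) | Power at d = 0.30 | Detectable d at 90% | N for 90% |
|---|---|---|---|---|
| 2:1 | 9.661 | 82.6% | 0.336 | 526 |
| 36:24 | 10.040 | 85.4% | 0.323 | 487 |
| 1:1 | 10.247 | 86.7% | 0.316 | 467 |

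The noncentral t gives 82.4%, 85.2% and 86.6%. The gap to 90% is 7.4, 4.6 and 3.3 points.

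**Step 4: can another reading give 90%?**
- Rounding: d = 0.305 gives 83.8% (2:1) to 87.8% (1:1).
- One-sided .05: 89.5% (2:1) and 91.4% (36:24), but section E says two-sided.
- No exclusions, 72 x 7 = 504: 88.8% (2:1) or 92.0% (1:1), but E.5 conditions on 420.

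**Step 5: are the two effects equal?** d = r/sqrt(p(1 - p)(1 - r^2)) at r = .16 gives 0.344 (2:1), 0.331 (36:24) and 0.324 (1:1).

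**Step 6: is 420 a minimum for the treatment terms?** The ICCs here are assumptions, because the documents give none, and compound symmetry is assumed.

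*Overall group difference on daily records:* effective N = 3,360/(1 + 55 x ICC). This is 896 at ICC 0.05, 517 at 0.10 and 280 at 0.20. It equals 420 at ICC = (3,360/420 - 1)/55 = 7/55 = 0.127.

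*Within-person change, 42 treatment days against 14 baseline days, d in daily-SD units:* effective N = 60/v, with v = (1 - ICC)(1/14 + 1/42) + s. Here s is the person-to-person variance in true change, as a fraction of daily variance.
- With s = 0, effective N is 630 at ICC 0, 900 at 0.3, 1,260 at 0.5 and 2,100 at 0.7.
- With s = 0.10 and ICC 0.2, v = 0.0762 + 0.10 = 0.1762 and effective N is about 341.
- It falls below 420 once v exceeds 60/420 = 0.1429, that is s above 0.048 at ICC 0 or above 0.095 at ICC 0.5.

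The answer therefore depends on the term tested and on quantities that E.5 does not state.

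**The case against.** The strongest defence is that the shortfall is small. Power stays above 80% at all three splits, and no 90% target is set outside E.5. E.5 also expects more than 420. An effective N of 467 to 526, equivalent to 10 to 20% less error variance (1 - 420/467 and 1 - 420/526), would restore 90% at d = 0.30. This limits the practical consequence, and it stands. It does not rescue the sentence, which states the power at 420 itself, and E.5 does not quantify the expected gain.

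A second defence is that a treatment-by-week contrast removes stable differences between people, so its effective N can be well above 420, as step 6 shows. That also stands, and it is why 420 cannot be called too high.

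A reader might infer more than the documents support:
- **That the trial is underpowered for treatment effects.** No ICC or variance of change is given, and plausible assumptions fall on both sides of 420. Rescaling d to the SD of weekly values can make power look far lower, but E.3 attaches daily outcomes to the treatment model.
- **That 60 is too optimistic because it deducts only sustained abstainers.** D.6 has 48 and 24 participants entering the experimental period on day 15, D.6.1 withdraws poor diary completers before treatment because they are the ones likely to be lost, and E.1 uses all available data. An explicit allowance is missing detail, not an error.
- **That the statements of full and adequate power in D.1 and D.2 are contradicted.** A gap of 3 to 7 points that leaves power above 80% does not show that.

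**Conclusion.** The treatment-effect figure in E.5 is wrong as written. This part rests only on the plan's own alpha, effective N and effect size, plus the split between arms; it needs no ICC. The association figure is right if 420 is accepted as the effective sample size.

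The description of 420 as a minimum likely to be exceeded is unsupported for the treatment and treatment-by-week terms. The direction of any error there cannot be determined from the documents. This part is an omission in the justification and is not evidence of low power.

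The firm error is modest and cheap to correct.

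**What to change.** In E.5:
- Replace the treatment-effect figure with 83 to 87% power at d = 0.30, or 90% power at d of about 0.32 to 0.34, naming the split between arms.
- Keep r = .16 for associations. Say that both figures are conditional on 420 being the effective sample size.
- Limit the minimum claim, and the expectation of exceeding it, to the week-to-week change predictor from which 420 is derived. To extend it to the treatment and treatment-by-week terms, add a calculation for those terms that states the SD scaling d, a range for the ICC, and the assumed person-level variance in change.

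The cost is a few sentences, plus a short calculation only if the wider claim is to be kept. Enrolment, model, alpha and estimand do not change, and D.1 and D.2 need no rewording on this account. The downside is a slightly less favourable stated figure.
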